## 6.2 Population pharmacokinetic analysis

NONMEM software (version 7.3, GloboMax LLC, Hanover, MD) will be used for population PK analysis. A stepwise approach will be following in the model building process: (i) determination of the structural base model; (ii) selection of the best fit statistical error model (iii) development of covariate model, (iv) and finally model evaluation.

**(i) Determination of the structural base model:** Different structural models based on one, two or three compartment will be fitted to the concentration-time data using NOMEMEM subroutines. Both linear and/or Michaelis–Menten kinetics will be assessed for elimination and distribution of the drug. Also linear and/or non-linear binding to plasma proteins will be considered.

**ii) Selection of statistical error models:** Inter-individual variability will be assumed to follow a log-normal distribution. For the residual error model additive, proportional and a combination of additive and proportional models will be tested.

**(iii) Development of covariate model:** Available clinical covariates will be assessed for biological plausibility and subsequently evaluated in the covariate analysis. Selected covariates will be tested on the structural model parameters (volume(s) of distribution and clearance). Standard covariate evaluation algorithms will be followed through forward addition and backward elimination or a combination of forward addition and backward elimination in a stepwise fashion.

**(iv) Model evaluation:** Diagnostic plots and statistical examination through objective function values will be used for comparison of models. Diagnostic plots will include scatter plot of residuals versus predicted values, scatter plot of observed values versus predicted values and scatter plot of weighted residuals versus explanatory variables. Objective functions will include log-likelihood ratio test for nested model. A decrease in objective function value by greater than 3.84 (which corresponds to  $p < 0.05$  based on chi-square test) will be considered statistically significant. Other objective function values also, Akaike Information Criterion (AIC) or Bayesian Information Criterion (BIC) will be examined. Finally, the stability of the final model will be assessed by the nonparametric bootstrapping method.

**v) Dosing Simulation:** Subsequent to population PK analysis, Monte Carlo simulations will be performed using either CLSI or EUCAST MIC interpretive criteria for the presumed or confirmed etiologic organisms, or specific MICs if available.

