## **3. OBJECTIVES**

- To describe the pharmacokinetics of intravenous posaconazole in critically ill patients
- To assess the influence of critical illness on the pharmacokinetics of posaconazole administered via intravenous infusion
- To assess the impact of altered plasma protein concentrations/binding in the critically ill on the pharmacokinetics of posaconazole

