## **5.2 Patient enrolment**

Patients that meet all the inclusion criteria and none of the exclusion criteria will be approached for informed consent. Investigators of the study will explain the procedures of the study verbally in addition to the structured patient information sheet that will be provided for the participants prior to consenting. The participants' next of kin will be approached if any of the participants are not in a position to give consent due to medical sedation or unconsciousness or severe illness. A total of 8 patients will be enrolled.

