## **7. STATISTICAL ANALYSIS AND SAMPLE SIZE JUSTIFICATION**

All data analysis will be performed by the investigator and his research team. Power calculation is not applicable for this prospective initial pharmacokinetic investigation in ICU patients. The planned pharmacokinetic data analysis and associated statistical considerations are as described above under the study procedures. We have performed previous studies with the proposed sample size for similar antimicrobial agents and have provided clinically meaningful results.

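### Stepwise covariate selection in 8 patients overstates the effects it keeps, and the plan asks for no estimate of those it drops, so it is a weak basis for objective 2 and the covariate part of objective 3

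*Combined protocol and SAP*

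**What the plan says.** Section 3 sets the second objective as "To assess the influence of critical illness on the pharmacokinetics of posaconazole administered via intravenous infusion". The third objective asks the same about altered plasma protein concentration or binding.

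Section 6.2(iii) gives the step that links patient characteristics to the model parameters. On the candidates it says "Available clinical covariates will be assessed for biological plausibility and subsequently evaluated in the covariate analysis". On the search it says "Standard covariate evaluation algorithms will be followed through forward addition and backward elimination or a combination of forward addition and backward elimination", applied stepwise to clearance and volume(s). Neither the candidates nor their number is fixed, and the choice among the search variants is left open.

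Section 6.2(iv) gives the threshold: "A decrease in objective function value by greater than 3.84 (which corresponds to" p < 0.05 on a chi-square test). It adds that "Akaike Information Criterion (AIC) or Bayesian Information Criterion (BIC) will be examined", without a decision rule, and that a nonparametric bootstrap will check the stability of the final model.

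On size, section 5.2 says "A total of 8 patients will be enrolled", and section 7 says "Power calculation is not applicable for this prospective initial pharmacokinetic investigation in ICU patients".

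Two other provisions bear on objective 3. Section 6 analyses both total and unbound concentrations, and section 6.2(i) considers linear and non-linear protein binding in the structural model.

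No covariate is to be kept regardless of significance. The plan does not say what is to be reported for a covariate that is not selected.

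**The concern.** Assessing an influence calls for an estimate and a statement of its uncertainty. A search that keeps a covariate only when its observed effect clears a threshold gives something else. The effects it keeps are biased away from zero, because they were kept for looking large. The effects it drops leave the model, and the plan asks for no estimate or interval for them.

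With 8 patients the threshold is high, so both problems could be substantial. A chance or overstated covariate could then be published as the effect of critical illness, and could enter the dosing simulations in section 6.2(v), which follow from the population model. A real effect could go unreported.

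**Working it through.** **Inputs from the documents.** n = 8 (section 5.2); threshold 3.84 (section 6.2(iv)); parameters are clearance and at least one volume (section 6.2(iii)).

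**Assumptions.** The documents give no effect size or between-patient variability. True correlations of 0.3 to 0.7 between covariate and log-parameter are therefore assumed. Sampling is taken to be rich enough that each patient's parameter is known without error, and the effect is taken as linear on the log scale.

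**1. The plan's own figure.** P(chi-square on 1 df > 3.84) = 0.050, so the stated correspondence is reproduced.

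**2. What a covariate must show in 8 patients.** Under the approximation the objective function drop is −8·ln(1 − r²). Setting this above 3.84 gives |r| > √(1 − e^(−3.84/8)) = √(1 − 0.619) = 0.617.

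**3. True error rate of that threshold.** t = 0.617·√6/√(1 − 0.381) = 1.92 on 6 df, two-sided p = 0.103. An exact 5% threshold would be 8·ln(1 + 2.447²/6) = 5.54.

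**4. Retention and inflation.** One covariate tested alone, by simulation. Inflation is the mean absolute retained slope divided by the true slope.

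| True correlation | Retained at 3.84 | Inflation at 3.84 | Retained at 5.54 | Inflation at 5.54 |
|---|---|---|---|---|
| 0.3 | 20% | 2.6 | 11% | 2.8 |
| 0.5 | 38% | 1.6 | 25% | 1.7 |
| 0.6 | 52% | 1.3 | – | – |
| 0.7 | 69% | 1.2 | – | – |

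A correctly calibrated threshold therefore does not cure the problem. Where it was calculated, retention falls and inflation rises.

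**5. Chance findings.** Section 5.5 lists four general severity items (APACHE II, SOFA, shock, ventilation). It also lists eight renal or hepatic markers (serum creatinine, urinary creatinine clearance, ALT, AST, ALP, GGT, INR, bilirubin). The plausibility screen might leave 4 of these or all 12. If all are noise and are tested on two parameters, the chance that at least one passes is as follows.

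| Candidates | 3.84, independent | 3.84, mutual correlation 0.6 | 5.54, independent | 5.54, mutual correlation 0.6 |
|---|---|---|---|---|
| 4 | 1 − 0.897⁸ = 58% | 49% | 1 − 0.95⁸ = 34% | 28% |
| 12 | 1 − 0.897²⁴ = 93% | 75% | 1 − 0.95²⁴ = 71% | 52% |

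The range is about 49% to 93% at 3.84, and 28% to 71% at an exact 5% threshold. The independent columns treat the tests as independent, and the correlated columns are simulated.

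**6. A pre-specified covariate that is always kept.** In the same simulation the mean estimate is 1.00 times the truth for correlations 0.3 to 0.7, and the 95% interval covers 95%. At correlation 0.5 the median half-width is about 1.6 times the true slope, so the bias goes but the imprecision stays.

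**7. Width of the interval.** If the between-patient SD on the log scale is 0.4 (assumed), the factor per SD of covariate is exp(t·0.4/√7):
- one covariate, t = 2.447 on 6 df: exp(0.370) = 1.45;
- two uncorrelated covariates, t = 2.571 on 5 df: exp(0.389) = 1.475;
- two covariates correlated 0.5: exp(0.389/√0.75) = exp(0.449) = 1.57.

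**The case against.** Stepwise covariate building is a conventional choice in a small first pharmacokinetic study, and section 7 describes the work as initial. That is fair, and it supports keeping the search as exploration. It does not make selected estimates unbiased. AIC and BIC are themselves selection criteria. The bootstrap is applied to the final model, after selection, and no correction for selection is stated.

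Four stronger readings are tempting, and the documents do not support them:

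- **That inflation of 1.6-fold, with most real effects dropped, is a property of the design.** It holds only near an assumed correlation of 0.5. From 0.6 upwards most effects are retained and the inflation is about 1.3 or less.
- **That the plan will report only retained covariates and read the rest as having no influence.** No such rule is written. The gap is the absence of any reporting rule.
- **That stepwise selection is the only route to objective 3.** The unbound concentrations and the structural binding models also serve it. They do not commit the plan to an estimate, with interval, of how protein differences between patients change clearance or volume.
- **That a chance finding is near certain.** The highest figures need 12 candidates and the 3.84 threshold. The Introduction expects little effect of renal or hepatic impairment, so the plausibility screen could remove eight of the 12.

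The calculation also ignores residual error and shrinkage in the mixed model. Uncertainty in individual parameters would generally lower retention and raise inflation, so this does not rescue the plan.

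**Conclusion.** The point holds, with limits. For objective 2 and the covariate part of objective 3, the plan relies on significance-driven selection from an unlisted set in 8 patients. For assumed true correlations of 0.3 to 0.7, retention runs from about 20% to 69%, and retained estimates average 2.6 down to 1.2 times the truth. Non-retention is not evidence of no influence.

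These sizes rest on the rich-data approximation and the assumed correlations. The direction of the bias does not depend on which correlation is chosen, and moving to an exact 5% threshold does not remove it. The change should be made before the covariate analysis. It does not touch the choice of structural model.

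A reader might infer that a better covariate analysis would fully answer objective 2. It would not. Every patient is in ICU, so a severity effect is a gradient among ICU patients, not the comparison with ward patients raised in section 2.

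**What to change.** In section 6.2(iii):

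- Pre-specify one illness-severity measure already collected, for example SOFA or APACHE II, and one named plasma-protein measure. Add the protein measure explicitly to the section 5.5 data sheet, which refers only to chemistry data in general.
- Report the effect of each on clearance and volume as a ratio with a 95% interval (profile-likelihood or t-based), whether or not it passes 3.84.
- State that non-retention is not evidence of no influence, and that the severity effect is a gradient within ICU patients.
- Keep the stepwise search as labelled exploration, and report that its retained effects are subject to selection bias.

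The cost is analysis wording plus one named item on the data sheet, with no more patients. The downside is that intervals of about ×/÷ 1.45 to 1.6 per SD of covariate (if the between-patient SD is 0.4) will be shown openly, and all other covariates become exploratory.

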## 4. STUDY DESIGN

This is a prospective, observational, pharmacokinetic study. The study will enrol eight patients with presumed or confirmed systemic fungal infections, who are admitted to ICU. Patients aged greater than 18 years with established central venous access for drug administration and no history of allergy for triazole antifungals will be approached for enrolment if they have not taken posaconazole within two weeks of time and if they are not pregnant. A single dose of 300mg IV posaconazole will be administered to eight study participants. Serial blood samples will be collected at pre-defined time points for determination of both total and unbound plasma concentrations. Structured data collection sheets will be used to collect other clinical data. The data generated will be subject to population pharmacokinetic analysis using computer software. Monte Carlo simulations will be performed to describe dose-exposure relationships.

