## 5.4 Sample collections

Serial blood samples will be collected just before and after administration of the single dose of posaconazole. The first sample will be collected immediately before commencing of the posaconazole infusion. The next three samples will be collected during drug infusion at 15 min, 45min and 75 minutes after commencing the infusion. The fifth sample will be taken at the end of line flushing (15-20min) after the 90 minutes infusion. The next samples will be taken at 3h, 5h, 8h, 12h, 18h, 24h, 30h, 36h and 48h after the commencement of drug infusion. The actual time of collection for individual samples will be recorded and used for analysis. Lithium heparin tubes will be used for sample collection. The volume of each blood samples will be 2-3ml. The plasma will be separated by centrifugation (3000 rpm for 10 minutes) and frozen under - 80°C for storage until the subsequent assay of total and unbound posaconazole concentration.

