## 5.5 Clinical data collection

Patients' electronic and paper based medical records will be reviewed to collect clinical data including demographic characteristics, list of diagnosis, microbiological data, vital signs, and clinical haematological and chemistry data. A structured data collection sheet will be used to collect these patient specific clinical data, which will include the following:

- Physical examination including vital signs
- ICU and Hospital admission and discharge dates and times
- Acute Physiology and Chronic Health Evaluation II [APACHE II] score and risk of death at ICU admission, APACHE II diagnosis upon recruitment
- Sequential Organ Failure Assessment [SOFA] score at ICU admission and daily during ICU antibiotic course
- Presence of shock on days of sampling
- Presence of mechanical ventilation
- Serum creatinine concentrations
- Urinary creatinine clearance (if available)
- Hepatic function markers (alanine aminotransferase (ALT), aspartate aminotransferase (AST), alanine phosphatase ALP), gamma glutamyl transferase (GGT), international normalised ratio (INR), bilirubin
- Medication list on days of sampling
- Antimicrobial Data: type, dose, dosing interval, duration of infusion
- RRT data:
  - Filter type, filter size, filter age at time of sampling

- Blood flow rates
- Dialysate dose
- Haematocrit
- Pre/post dilution dose
- Patient fluid balance on day of sampling and targeted hourly fluid removal
- Changes made to settings during sampling interval
- Transmembrane pressure
- Infection data:
  - Organisms isolated and sample type,
  - Minimum inhibitory concentration if available

All case report forms and other data (including without limitation, written, printed, graphic, video and audio material, and information contained in any computer database or computer readable form) created or developed in connection with the Study will be owned by the Principal Investigator. All data will be collected by study research staff.

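### With 8 patients, an OFV drop of 3.84 can be a test at about 10% to 14%, not 5%, for a covariate that is fixed within a patient

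*Combined protocol and SAP*

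**What the plan says.** Section 6.2(iv) gives one numerical rule for comparing nested models: "A decrease in objective function value by greater than 3.84 (which corresponds to" p < 0.05 by the chi-square test, and such a drop counts as statistically significant. Section 6.2(iii) takes covariates into the model by stepwise selection: "Selected covariates will be tested on the structural model parameters (volume(s) of distribution and clearance"), and "Standard covariate evaluation algorithms will be followed through forward addition and backward elimination", or a combination of the two. No cut-off other than 3.84 is given for either direction.

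The size of the study is fixed: "A total of 8 patients will be enrolled" (section 5.2; section 4 agrees). Section 5.5 lists covariates that take one value per patient, for example "Acute Physiology and Chronic Health Evaluation II [APACHE II] score and risk of death at ICU admission".

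Other checks in section 6.2 are a screen for biological plausibility, diagnostic plots, AIC or BIC, and a bootstrap of the final model. Section 7 describes an initial investigation without a power calculation and refers back to the methods already described.

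**The concern.** The chi-square reference is an approximation that improves as the number of independent units grows. Each patient gives 14 samples, which may look like ample data. But a covariate with one value per patient is compared across patients only, and repeated sampling adds no patients. Eight is few for a maximum-likelihood ratio test, and the error is in the direction of too many false positives.

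Covariate effects are a main way for this plan to address its second objective, "To assess the influence of critical illness on the pharmacokinetics of posaconazole administered via intravenous infusion", and they also bear on the third, on altered plasma protein concentration and binding. A covariate reported at p < 0.05 under this rule could carry two to three times the stated chance of being a false signal. The population model also precedes the Monte Carlo dosing simulations, so a falsely retained covariate could pass into them.

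**Working it through.** **Inputs.** Patients n = 8 (sections 4 and 5.2). Cut-off 3.84 and nominal level 0.05 (section 6.2(iv)). Log-normal inter-individual variability (section 6.2(ii)), so the log of an individual parameter is normal. Samples after the start of infusion: 3 during infusion + 1 after the flush + 9 later = 13 per patient (section 5.4).

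**The plan's own figure.** The upper tail of chi-square with 1 degree of freedom at 3.84 is 0.0500. The stated conversion reproduces as a large-sample figure.

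**Small-sample level, one random effect.** Suppose that the individual log-parameters are well determined by the data. Testing a patient-level covariate is then a normal regression on 8 values. For the k-th covariate on a parameter,

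OFV drop = n × ln(1 + F/df), with df = n − 1 − k,

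so a cut-off c is the same as F(1, df) > df × (exp(c/n) − 1). Here exp(3.84/8) − 1 = 0.616.

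- First covariate, df = 6: F > 6 × 0.616 = 3.70, true level **10.3%**.
- Second covariate on the same parameter, df = 5: F > 5 × 0.616 = 3.08, true level **14.0%**.
- By the same formula the first-covariate level is 5.6% with 50 patients, so the problem is one of this sample size.

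**Two random effects with a full covariance** (for example on clearance and volume). A covariate on one parameter is then tested conditionally on the other parameter, which uses one more degree of freedom. A first covariate is therefore already at df = 5, a level of about **14%**. Simulation with 8 patients and known individual parameters gave 14.0%.

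**When residual error is not negligible.** A balanced random-intercept model fitted by maximum likelihood, 8 patients × 13 samples, 40,000 runs per setting, cut-off 3.84. The SDs are on the log scale and are assumptions.

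| Between-patient SD | Residual SD | Ratio | First covariate | Second covariate |
|---|---|---|---|---|
| 0.4 | 0.2 | 0.5 | 10.4% | 14.3% |
| 0.4 | 0.4 | 1 | 10.3% | 13.4% |
| 0.3 | 0.5 | 1.7 | 9.9% | 13.2% |
| 0.2 | 0.8 | 4 | 7.5% | 9.2% |
| 0.1 | 1.0 | 10 | 4.7% | 5.4% |

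**Would another fixed cut-off do?** With uncorrelated random effects, a 5% test needs a drop of about 5.54 for a first covariate and 6.74 for a second. With a full covariance of two random effects, 5.54 gives F > 5 × (exp(5.54/8) − 1) = 4.99 on (1, 5) degrees of freedom, a level of 7.6%. The right cut-off thus depends on a random-effects structure that the plan has not yet chosen.

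**Do the other checks repair the level?** The plausibility screen limits which covariates are tried, not the level of each test. An AIC improvement needs a drop above 2 for one added parameter: F > 6 × (exp(2/8) − 1) = 1.70, a level of about 24%. The bootstrap examines the stability of the final model, after selection. None of these recalibrates 3.84.

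**The case against.** The strongest reply is that the plan uses a customary convention and applies it correctly as a chi-square figure, in an initial study where no efficacy or confirmatory claim depends on it. This stands in part. A reader might infer that the sponsor has miscalculated; it has not, since 3.84 does give 0.05 in large samples. The fault is in attaching that p-value to a test with 8 independent units.

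A second reply is that 10% is no more a fact than 5%. This also stands. The figure needs maximum-likelihood estimation, a random effect on the tested parameter, a covariate constant within a patient, and individual parameters that the data determine well. Thirteen samples over 48 hours make the last condition plausible. How well they determine a peripheral volume was not examined. The calculations are linear-model analogues; no NONMEM model was run.

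Three stronger readings are tempting and not supported:

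- That the plan should simply replace 3.84 by 5.5 and 6.7. Those values hold only for uncorrelated random effects and can themselves miss 5%, as shown above.
- That the same inflation affects the choice between one, two and three compartments. The documents give no basis for a material error there. A simple simulation of one against two compartments, under assumed PK values, gave 5.4% at 3.84 (Monte Carlo 95% interval 3.4% to 7.4%), which is compatible with 5%.
- That every covariate is affected. Covariates that change within a patient over the sampling period, such as daily SOFA, lie outside the argument.

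**Conclusion.** The concern holds for covariates that are fixed within a patient. Under the stated rule the true level of a single test is about 10% with one random effect on the tested parameter. It is about 14% for a second covariate on that parameter, or for a first when two random effects have a full covariance. In the settings tried, it remained near 10% for a first covariate with residual SD up to about 1.7 times the between-patient SD. It fell to about 7.5% at 4 times and to about 5% at 10 times. The documents give neither SD, so the direction is firm and the exact level is conditional.

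Nothing else in the plan corrects the level. Because the study is exploratory, the consequence is limited to how covariate findings for the second and third objectives are read. It does not invalidate the description of the pharmacokinetics. The change is worth making because the plan itself attaches the p-value.

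**What to change.** In section 6.2(iii) and (iv):

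1. Describe 3.84 as a nominal, large-sample screening cut-off for one added parameter.
2. For any patient-level covariate reported as significant, give a p-value from permuting the covariate across the 8 patients, or from simulating data under the final model without that covariate and refitting with and without it.
3. Where neither is done, do not attach p < 0.05. Report the effect as exploratory, with its interval.

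The values 5.5 and 6.7 may be quoted as illustrations for uncorrelated random effects, not as fixed cut-offs.

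**Cost.** A change of wording and some extra model runs; no change to patients or samples. Fewer covariates will be declared significant, and some real effects will be missed. In the one-random-effect case, a sample correlation of at least √(1 − exp(−3.84/8)) = 0.62 passes 3.84, against √(1 − exp(−5.54/8)) = 0.71 for a true 5% test. Permutation also has a floor: for a yes/no covariate present in 1 of 8 patients there are 8 arrangements, so the smallest p is 1/8 = 0.125 and 5% cannot be reached. With 2 of 8 there are 28 arrangements and the smallest p is 1/28 = 0.036. For a covariate present in a single patient, the simulation route or a purely exploratory report is what remains.

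### Section 6.2(iv) labels an objective-function drop above 3.84 as p < 0.05 for every nested comparison, but that holds only for one added parameter, and each extra compartment adds at least two

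*Combined protocol and SAP*

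**What the plan says.** Section 6.2(i) of the combined protocol and SAP describes the structural search: "Different structural models based on one, two or three compartment will be fitted to the concentration-time data". Linear and Michaelis–Menten kinetics are also assessed, and "Also linear and/or non-linear binding to plasma proteins will be considered". On random effects, 6.2(ii) says only that "Inter-individual variability will be assumed to follow a log-normal distribution". It does not say which parameters will carry them.

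Section 6.2(iv) sets the comparison rules. "Diagnostic plots and statistical examination through objective function values will be used for comparison of models". For nested models, "Objective functions will include log-likelihood ratio test for nested model". The only numerical criterion is "A decrease in objective function value by greater than 3.84", which the plan equates with p < 0.05 on a chi-square test and which "will be considered statistically significant". In addition, "Akaike Information Criterion (AIC) or Bayesian Information Criterion (BIC) will be examined", and the final model is bootstrapped. The plan gives no degrees of freedom, no second cut-off for steps that add more than one parameter, and no order of precedence among the criteria.

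**The concern.** The critical value of a likelihood ratio test depends on how many parameters the larger model adds. The value 3.84 suits a single covariate coefficient. It does not suit the step from one to two compartments or from two to three. In standard pharmacokinetics each such step brings in an inter-compartmental clearance and a peripheral volume, and more if between-patient variability is placed on them. The p-value label is therefore wrong as written for those comparisons, and it errs towards accepting the larger model.

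Sampling stops at 48 h (Section 5.4), so anything later is extrapolated from the chosen structure. Section 6.2(v) carries that structure into Monte Carlo dosing simulations, and the Introduction presents the PK analysis as the basis for designing ICU regimens. A compartment accepted by chance could change the extrapolated terminal phase.

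**Working it through.** **Inputs from the protocol.** Cut-off 3.84 and stated level 0.05 (6.2(iv)); one, two or three compartments (6.2(i)); 8 patients (5.2); 13 samples per patient after the start of infusion (5.4: three during infusion, one at the end of flushing, nine from 3 h to 48 h), so 8 × 13 = 104 observations. Two structural parameters per added compartment is standard pharmacokinetics and is not stated in the plan.

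**Step 1: the plan's own figure.** With 1 df, P(χ² > 3.84) = 0.0500. The stated p < 0.05 reproduces, but only for one added parameter.

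**Step 2: the same cut-off with more parameters.**
- 2 df: exp(−3.84/2) = exp(−1.92) = 0.147.
- 3 df: 0.0500 + √(2 × 3.84/π) × exp(−1.92) = 0.0500 + 1.5635 × 0.1466 = 0.279.
- 4 df: exp(−1.92) × (1 + 1.92) = 0.428.

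The 3 and 4 df rows apply if one or two variability terms come with the new compartment. The 5% points are 3.84 (1 df), 5.99 (2 df, = −2 ln 0.05), 7.81 (3 df) and 9.49 (4 df).

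**Step 3: do AIC or BIC close the gap?** For two added parameters:
- AIC needs a drop of 2 × 2 = 4.0, a nominal level of exp(−2) = 13.5%, almost the same as 3.84.
- BIC needs a drop of 2 ln n, a nominal level of 1/n. With n = 8 patients that is 4.16 and 12.5%. With n = 104 observations it is 9.29 and about 1.0%.

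The plan does not say which n applies, or whether AIC or BIC overrides 3.84.

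**Step 4: how far to trust the nominal levels.** Under the smaller model the inter-compartmental clearance lies on its boundary (zero) and the peripheral volume is not identified. The chi-square reference therefore does not strictly hold, and the rates were checked by simulation at the protocol's sample times. All PK values are assumptions.

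*False third compartment.* Linearised mixed-effects fits, two-compartment truth; CL 8 L/h, V1 60 L, Q 30 L/h, V2 180 L; between-patient SD 0.4, 0.3 and 0.4 on CL, V1 and V2; residual error 12%. Three independent sets of runs:

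| Datasets | Drop > 3.84 | Drop > 4.0 (AIC) | Drop > 5.99 |
|---|---|---|---|
| 222 | 12.6% (SE 2.2) | 10.8% | 5.9% (SE 1.6) |
| 300 | 14.3% (SE 2.0) | 12.0% (SE 1.9) | 5.0% (SE 1.3) |
| 1,744 | 9.4% (SE 0.7) | 8.7% | 3.6% |

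The largest set used only three starts for the expanded model and may be slightly low. In that set a false third compartment passed the observation-based BIC in 0.8% of datasets.

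*False second compartment.* One-compartment truth:

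| Model | Datasets | Drop > 3.84 | Drop > 5.99 |
|---|---|---|---|
| Pooled, 20% residual, CL 7 L/h, V 250 L | 1,000 | 6.3% | 2.4% |
| Pooled, 20% residual, CL 15 L/h, V 250 L | 1,000 | 8.0% | 2.9% |
| Mixed-effects, CL 8 L/h, V 240 L | 300 | 5.7% (SE 1.3) | 2.3% |

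**The case against.** The strongest reply has four parts.

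*The nominal levels are not error rates.* This stands. A reader might infer that structural selection as a whole runs at 13–15% error. The documents do not support that: 14.7% is the nominal tail at exactly two added parameters, regularity fails, and the simulated rate for one versus two compartments is close to 5%. A reader might also conclude that random effects double the error, because the pooled rates are about half the mixed-effects rates for a third compartment. That is not shown either. Those two sets differ in the comparison tested as well as in the random effects, and the mixed-effects run of one versus two compartments gave 5.7%.

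*The cut-off is not the only criterion.* This is correct: plots, AIC or BIC, and a bootstrap of the final model are all named. Observation-based BIC would be stricter than 5.99. But the plan does not commit to that version or let it decide, and AIC gives almost no extra protection. The cut-off of 3.84 is the only rule that the plan ties to significance.

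*The consequence may be small.* This largely stands. In the 1,744-dataset set, among falsely accepted third compartments the median ratio of estimated clearance (expanded to base model) was 0.99, with quartiles 0.92 to 1.01. About a tenth fell below 0.6, which is roughly 1% of all datasets (0.1 × 9.4%). Serious distortion is possible but uncommon.

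*No claim rests on the number of compartments.* This also stands. A reader might expect a chance compartment to be reported as a significant finding, but no hypothesis or objective in Sections 2 and 3 concerns compartment number, and Section 7 describes an initial PK investigation without a power calculation.

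**Conclusion.** The point holds as a degrees-of-freedom gap in 6.2(iv). The equation of 3.84 with p < 0.05 is right for one added parameter and wrong as written for compartment comparisons, where the nominal level is 14.7% with two added parameters, 27.9% with three, and more beyond that. The nominal figures need only the chi-square distribution and the standard parameter count.

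The actual false-acceptance rate is uncertain. Under assumed PK values it was about 9–14% for a third compartment and about 6–8% for a second, and other values could move both ranges. The practical effect is modest in a descriptive 8-patient study. The correction is still worth making, because the selected structure is carried into the dosing simulations and the plan does not say which criterion prevails when they disagree.

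**What to change.** In 6.2(iv), replace the single figure with wording such as:

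> For nested models the cut-off for the drop in OFV depends on the number of parameters added: 3.84 for one, 5.99 for two and 7.81 for three (5% level). The number added will be listed for each structural comparison. The value 3.84 applies to one-parameter steps such as a single covariate coefficient. AIC or BIC and diagnostic plots remain additional criteria.

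AIC and BIC should not be confined to non-nested models: counted on observations, BIC is the strictest criterion that the plan names. The text should state which n BIC uses.

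The cost is a few lines of text, with no change to data collection. The downside is a slightly lower chance of accepting a true but weakly supported compartment. For one versus two compartments 5.99 is conservative: a false second compartment passed it in 2.3–2.9% of simulated datasets.
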